8.3 Method for Assigning Subjects to Treatment Groups

REDCap will be used to randomize patients to one of two groups based on when providers will intubate (TOFC=1 and 2 minutes after rocuronium at 0.6 mg/kg).

8.4 Masking/Blinding of Study

This is an open-label pilot investigation. Masking and blinding procedures are not applicable.

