4.1 Abstract

Neuromuscular blocking agents (NMBAs) are a commonly utilized class of medications in the perioperative setting that can help facilitate endotracheal intubation, optimize surgical conditions, and assist with mechanical ventilation. Experts recommend the use of quantitative (or objective) neuromuscular monitors whenever NMBAs are utilized because these devices are the only method for reliably determining adequate neuromuscular paralysis and recovery of neuromuscular function. Unfortunately, several barriers exist that have prevented the widespread application of these devices, and many practitioners are still using qualitative (subjective) methods (i.e., use a peripheral nerve stimulator) as an assessment of neuromuscular blockade despite the lack of accuracy of subjective methods and the well-described morbidity and mortality associated with residual blockade. Objective monitors may also prove useful during the onset of NMB and provide useful information about when optimal intubation conditions have been reached.

The primary aim of this study is to compare intubating conditions at varying levels of rocuronium-induced neuromuscular blockade.

The TetraGraph (Senzime AB, Uppsala, Sweden) is an FDA-approved standalone EMG-based quantitative monitor that measures electrical activity within the muscle following peripheral nerve stimulation and is unaffected by involuntary patient motion or restricted muscle movements from surgical positioning. Following standard of care administration of propofol between 1 and 1.5 mg/kg and lidocaine between 0.5 and 1 mg/kg intravenously (IV) for induction of general anesthesia, the TetraGraph neuromuscular monitor will be calibrated, following which rocuronium at 0.6 mg/kg will be administered. Intubation will commence based on the one of two triggers based on randomization has been reached. One group will be intubated once the train-of-four count (TOFC) reaches 1 and the other when 2 minutes have passed. The time to intubation will be recorded and the intubating health care clinician will be surveyed about intubation conditions that includes variables such as: ease of laryngoscopy (jaw relaxation), vocal cord position and movement, airway reaction (coughing) and movement of the limbs ([Table 17.2](#)) The assessment will be done using video laryngoscopy display at the time of intubation.

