6.4 Primary Study Endpoints

Compare intubating conditions when patients are intubated at 2 different endpoints: TOFC=1; or 2 minutes after rocuronium at 0.6 mg/kg. The assessment of the intubating conditions will be evaluated by the healthcare providers using a scale ([Table 17.1](#)) that includes 4 variables (ease of laryngoscopy, vocal cord position, and reaction to tracheal tube insertion with 3 response options

per each evaluation. The composite score (1-3) will be compared between groups, with the lowest total score of 3 correlating with optimal intubating conditions and the highest score of 9 representing the worse possible intubating conditions. The scale has been validated previously. (25)

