8.2 Visit 2 (Randomization and Treatment – day of surgery)

- Induction of anesthesia is standardized to utilize lidocaine dose between 0.5 and 1 mg/kg, propofol between 1 and 1.5 mg/kg, and rocuronium at 0.6 mg/kg. Anesthesia will be maintained with sevoflurane at 1 minimum alveolar concentration (MAC) through the

induction and intubation sequence. Following induction but prior to rocuronium administration, TetraGraph will be calibrated, and the supramaximal current will be obtained as per standard of care practice.

- Prior to induction of anesthesia, the TetraGraph will be placed on the same arm as the IV catheter over the ulnar nerve and the thumb to measure the response of adductor pollicis nerve.
- Randomization will be performed utilizing REDCap and patients will be assigned to be intubated at TOFC=1 or 2 minutes after rocuronium administration.
- After NMBA administration, sets of measurements will be taken every 20 sec until the desired level of neuromuscular blockade has been reached or 2 minutes has passed since rocuronium administration, depending on the group. Once the level of blockade has been achieved or the appropriate time has lapsed, anesthesia providers will intubate the patient using video laryngoscopy.
- If the anesthesia team finds the intubating conditions to be unacceptable, bag mask ventilation will be continued until the anesthesiologists deems it appropriate to attempt laryngoscopy as per standard of care.
- Following intubation, perioperative care will be at the discretion of the anesthesiologist.
- When convenient for the anesthesia team, they will be surveyed about the ease of laryngoscopy. An independent observer will note the other 2 objective components of the survey.

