9.1 Sample Size Determination

Based on preliminary data, intubating score of 3 (ideal conditions) will occur in approximately 65% of patients in the two-minute group. With a sample size of 83 patients per group (166 patients total), we will have 80% power at the 5% significance level to detect a difference in this outcome of 20% (i.e. 65% vs. 85%) between the two-minute group and the other two treatment groups using a chi-square test. We will enroll 85 patients in each group (170 total) to account for possible dropouts.

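### Section 8.4 sets masking aside altogether, although section 8.2 already has an independent observer for two of the three primary items who could be kept unaware of the arm; sections 4.1 and 8.2 also disagree on who scores

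*Combined protocol and SAP*

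**What the plan says.** Section 8.4 calls the study open-label and says "Masking and blinding procedures are not applicable". The Study Summary and section 6.1 also describe it as open-label or unblinded.

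On who scores, three places speak:

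- Section 8.2 splits the scale. On ease of laryngoscopy: "When convenient for the anesthesia team, they will be surveyed about the ease of laryngoscopy". On the rest: "An independent observer will note the other 2 objective components of the survey". Read with Table 17.1, the other two components are vocal cord position and reaction to insertion of the tube and cuff inflation.
- Section 4.1 says "the intubating health care clinician will be surveyed about intubation conditions", and its list of variables includes the cords, coughing and limb movement. It mentions no observer.
- Section 6.4 says "The assessment of the intubating conditions will be evaluated by the healthcare providers using a scale". It mentions no observer and gives no time.

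On when, section 4.1 says "The assessment will be done using video laryngoscopy display at the time of intubation". Section 8.2 gives a time only for the laryngoscopy question, and that time is the team's convenience.

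The sample size in section 9.1 rests on a binary outcome: "intubating score of 3 (ideal conditions) will occur in approximately 65% of patients in the two-minute group".

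**The concern.** The person who intubates on a count or a clock cannot be masked to it. A separate assessor can be, at least in part, and section 8.2 already provides one. Section 8.4 nevertheless sets masking aside for everyone, gives no reason, and does not say whether the observer is told the arm.

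The outcome is sensitive to small rating differences. A total of 3 requires a 1 on every item, so a one-step change on one item moves a patient out of the success category. If knowledge of the arm tilts the ratings, even slightly, the tilt goes straight into the comparison.

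Sections 4.1 and 8.2 also cannot both be followed on the scorer. If the clinician rates everything, the observer's role disappears and no item could be masked at all.

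**Working it through.** **1. The plan's own figure.** Inputs from section 9.1: 65% versus 85%, 5% level (taken as two-sided), 80% power, chi-square test.

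- Without continuity correction: n = [1.960 × √(2 × 0.75 × 0.25) + 0.842 × √(0.65 × 0.35 + 0.85 × 0.15)]² / 0.20² = 72.4, so 73 per group.
- With continuity correction: n′ = (72.4 / 4) × [1 + √(1 + 4 / (72.4 × 0.20))]² = 82.1, so 83 per group.

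The stated 83 is reproduced with the correction and not without it. Section 9.1.1 does not say which form of the test will be used, so both are shown below.

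**2. The scorer, place by place.**

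| Item (Table 17.1) | Section 4.1 | Section 6.4 | Section 8.2 |
|---|---|---|---|
| Laryngoscopy | intubating clinician | healthcare providers | anesthesia team |
| Vocal cord position | intubating clinician | healthcare providers | independent observer |
| Reaction to tube | intubating clinician | healthcare providers | independent observer |

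The contradiction is between 4.1 and 8.2, on the second and third rows. The term in 6.4 is broad enough to include an observer, so it is vague rather than contradictory.

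**3. The time.** Section 4.1 gives the moment of intubation; 8.2 lets the laryngoscopy question wait. Section 6.4 gives no time, and 8.2 gives none for the observer's items. The difference therefore concerns one item and two places.

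**4. The items.** Section 6.4 announces four variables but lists three; 4.1 adds limb movement. Table 17.1 has three items, which fits the 3 to 9 range in 6.4.

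**5. Illustration of size.** Assumptions, none of them from the documents: no true difference, 65% scoring 3 in both arms, and unmasked rating that downgrades a fraction s of the would-be score-3 patients in one arm. Then p₁ = 0.65 and p₂ = 0.65 × (1 − s). With 85 per arm, 0.65 × 85 = 55.25 patients per arm would score 3. The rejection probability is the sum, over all possible 2×2 tables, of the probability of each table that is significant at two-sided 5%.

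| s | p₂ | Patients moved (55.25 × s) | Corrected test | Uncorrected test |
|---|---|---|---|---|
| 0 | 0.650 | 0 | 3.3% | 4.8% |
| 5% | 0.6175 | 2.8 | 5.1% | 7.0% |
| 10% | 0.585 | 5.5 | 10.7% | 13.9% |
| 15% | 0.5525 | 8.3 | 20.8% | 25.6% |

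**6. What masking the observer could recover.** Suppose the observer's two items carry a share f of a 10% shift and masking them works completely. The remaining shift is 10% × (1 − f).

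| f | Remaining shift | Corrected | Uncorrected |
|---|---|---|---|
| 0 | 10.0% | 10.7% | 13.9% |
| 1/3 | 6.7% | 6.5% | 8.8% |
| 1/2 | 5.0% | 5.1% | 7.0% |
| 2/3 | 3.3% | 4.1% | 5.8% |

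For f below one third, the residual lies between the first two rows. Partial masking would gain less than each row shows.

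**The case against.** The strongest reply has four parts.

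*Open-label status is declared.* True, and it is a legitimate choice for the operator. It does not explain why the separate observer should know the arm, and it does not settle who scores.

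*Masking may not be achievable.* The triggers are elapsed time and a monitor count, readings are taken every 20 seconds, and the documents do not say whether the observer also takes them. An observer in the room may see the display or guess the time. This stands: masking can only be partial, and the text must allow for its failure.

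*The observer's items are the least exposed.* This largely stands. In Table 17.1, none versus slight is no movement versus some, and moving cords already score 2. Only abducted versus intermediate in still cords has no written criterion. The operator's item stays unmasked and can change a total of 3 by itself. The unmasked team also controls when laryngoscopy is attempted: "If the anesthesia team finds the intubating conditions to be unacceptable, bag mask ventilation will be continued until the anesthesiologists deems it appropriate". So the share f may be small, and the gain with it.

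*The timing difference is trivial.* Mostly right. A rating formed at intubation can be collected shortly afterwards, and participation is limited to 15 minutes (section 6.3). It deserves one clarifying clause.

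A reader might infer that sections 4.1, 6.4 and 8.2 all conflict on both scorer and time. They do not: 6.4 gives no time, and its wording may cover an observer.

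**Conclusion.** The point holds as a cheap improvement. Section 8.4 excludes masking for an assessor to whom it could at least partly apply, and 4.1 contradicts 8.2 on who rates two of the three items behind the powered outcome. The mismatch in timing is minor and confined to laryngoscopy.

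A reader might go further and conclude that the trial's false-positive rate is 11% or 14%, or that masking the observer would restore 5%. The documents support neither. They give no shift size, direction or item share, so the tables are illustrations. With the continuity-corrected test, which matches the planned 83 per group, a 5% one-arm downgrade leaves the error at 5.1%, essentially nominal; a 10% downgrade gives 10.7%. If the observer's items carry less than one third of that 10% shift, even complete masking leaves 6.5% to 10.7% (8.8% to 13.9% uncorrected). The case rests on the low cost of the change, not on a demonstrated bias. No sample size figure is disputed.

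**What to change.** 1. **Section 8.4.** Replace the masking sentence with: *The intubating team is not masked. The independent observer named in 8.2 is not told the assignment and, where feasible, does not see the TetraGraph display or timer before scoring.* If the observer also takes the 20-second readings, say so there and report it as a limitation.
2. **Sections 4.1 and 6.4.** Align them with the split in 8.2. The observer scores vocal cord position and reaction to tube insertion and cuff inflation at intubation. The intubating clinician scores ease of laryngoscopy, recorded as soon after intubation as patient care allows, with the time noted.
3. **Item count.** Reconcile the four variables in 6.4 and the limb movement in 4.1 with the three items of Table 17.1.

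The cost is wording and one recorded time. No assessor is added, and neither the sample size nor any step of care changes. The limits should be stated openly: elapsed time can be guessed, and both the laryngoscopy item and the decision to attempt laryngoscopy stay unmasked. Bias is reduced, not removed.

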8.5 Schedule of Events

Schedule of Events		
Study Activity	Visit 1	Visit 2
Scheduled Intubation		X
Intubating conditions observation		X
Informed consent	X	
Review of Medical Record	X	
Adverse event evaluation		X

9 Statistical Plan

9.1 Sample Size Determination

Based on preliminary data, intubating score of 3 (ideal conditions) will occur in approximately 65% of patients in the two-minute group. With a sample size of 83 patients per group (166 patients total), we will have 80% power at the 5% significance level to detect a difference in this outcome of 20% (i.e. 65% vs. 85%) between the two-minute group and the other two treatment groups using a chi-square test. We will enroll 85 patients in each group (170 total) to account for possible dropouts.

9.1.1 Descriptive Statistics

Comparisons of intubating conditions will be made using a chi-square test.

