neuromuscular blockade utilizing EMG. Currently, our practice has significant heterogeneity in determining when the appropriate time to perform endotracheal intubation following induction of anesthesia. Following induction with propofol, rocuronium is administered and patients can have significantly varied response to this medication. Most providers wait approximately 2 minutes before intubating the patient's trachea. Given this drug's variable pharmacokinetics, quantitative monitoring may be used to objectively determine when optimal intubating conditions have been achieved. While use of these devices during induction of anesthesia represents best practice, it is rarely performed. In fact, it is very common to observe endotracheal intubation in a patient that has not yet had complete onset of neuromuscular blockade as evidenced by coughing or movement of the limbs following intubation. Further complicating the matter is that there is no method for objectively measuring the muscle groups that are important during intubation (oropharyngeal adductors and the diaphragm) and clinicians must make inferences about these muscle groups based on other muscle groups (adductor pollicis). Having a better understanding of the correlation between objective measurements at the hand and intubating conditions can provide anesthesia providers important information regarding the timing of endotracheal intubation.

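### The only planned comparison is a valid but unadjusted chi-square with no effect estimate or interval; recorded age, weight and height go unused, so some precision may be given up

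*Combined protocol and SAP*

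**What the plan says.** Section 9.1.1 of the combined protocol and SAP holds the whole comparison plan in one sentence: "Comparisons of intubating conditions will be made using a chi-square test". It does not use the word primary, but no other test is given and section 9.1 sizes the trial on the same one. There the planning rate is that an "intubating score of 3 (ideal conditions) will occur in approximately 65% of patients in the two-minute group", the target is a 20-point difference (65% v 85%), and with 83 per group "we will have 80% power at the 5% significance level". Enrolment is 85 per group.

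No section names a risk difference, a ratio, a confidence interval, a model or a covariate. Section 8.3 says "REDCap will be used to randomize patients to one of two groups based on when providers will intubate" and gives no stratification factor. The intraoperative form in section 17.2 has fields for age, weight and height. Section 4.2 rests the trial on differences between patients: "Given this drug's variable pharmacokinetics, quantitative monitoring may be used to objectively determine when optimal intubating conditions have been achieved".

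**The concern.** There are two separate matters here.

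First, a chi-square test returns a p-value. With 85 per group the uncertainty about the difference is wide, and a non-significant p-value could be read as showing that the two timing rules give similar conditions when the data still allow a large difference.

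Second, the rationale is that patients respond differently to the same weight-based dose, yet the analysis uses no patient characteristic. Age, weight and height cannot be changed by allocation and are already collected. If they predict the outcome, including them would narrow the interval and raise power with no extra patients.

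**Working it through.** **1. The plan's own figure.** Inputs from section 9.1: p1 = 0.65, p2 = 0.85, power 80%, 5% significance (two-sided assumed). With mean rate 0.75:

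n = [1.96 × √(2 × 0.75 × 0.25) + 0.8416 × √(0.65 × 0.35 + 0.85 × 0.15)]² / 0.20² = (1.200 + 0.501)² / 0.04 = 72.4, so 73 per group without continuity correction.

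With the correction: (72.4 / 4) × [1 + √(1 + 4 / (72.4 × 0.20))]² = 82.1, so 83 per group, as stated. At 85 per group the normal-approximation power is 81.5% corrected and 86.0% uncorrected. There is no sample-size error.

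**2. What the p-value leaves out.** Half-width of the unadjusted 95% CI at 85 per group = 1.96 × √[(p1q1 + p2q2) / 85]:

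- 65% v 65%: 1.96 × √(0.455 / 85) = 14.3 points
- 65% v 75%: 1.96 × √(0.415 / 85) = 13.7 points
- 65% v 85%: 1.96 × √(0.355 / 85) = 12.7 points

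Suppose 65% v 75% were observed. The uncorrected test gives z = 0.10 / √(0.70 × 0.30 × 2 / 85) = 1.42, p about 0.16. The interval is 10 ± 13.7, or about −4 to +24 points. It contains both zero and the 20-point design difference.

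**3. What adjustment could gain.** The prognostic strength of age and body size is not in the documents, so it is an assumption and a range is shown. All simulations use 85 per group and 65% v 85%, and compare a logistic model standardised to a marginal risk difference with the unadjusted analysis.

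Two covariates, 4,000 trials per setting:

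| Joint AUC | Variance ratio | Power, unadjusted to adjusted |
|---|---|---|
| 0.61 | 1.00 | no change |
| 0.66 | 0.95 | 87% to 89% |
| 0.70 | 0.92 | 87% to 90% |
| 0.74 | 0.88 | 87% to 91% |

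With useless covariates power was 86% either way. Type I error of the adjusted test was 5.1 to 5.3%.

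Three covariates, 4,000 trials per setting (adjusted power here is from the likelihood-ratio test for arm in the logistic model):

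| Combined log-odds SD | Variance ratio | Power, unadjusted to adjusted |
|---|---|---|
| 0 | 1.03 | 86.8% to 86.7% |
| 0.3 | 1.02 | 86.3% to 86.2% |
| 0.5 | 0.98 | 86.2% to 87.3% |
| 0.8 | 0.94 | 87.7% to 90.5% |
| 1.2 | 0.83 | 86.4% to 92.8% |

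The Monte Carlo standard error of each power figure is about √(0.86 × 0.14 / 4000) = 0.5 points.

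A further set gave variance ratios from 1.01 (useless covariates) to 0.90 (strong), power changes from about 0 to +3 points and type I error of 4.4 to 5.9%. It showed no loss when the covariates acted mainly in the two-minute arm.

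**4. In interval terms.** Multiplying 12.67 points by the square root of the variance ratio gives 12.9 at 1.03, 12.3 at 0.94, 11.9 at 0.88 and 11.5 at 0.83.

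**5. Can the model be fitted?** Expected patients without score 3: 85 × 0.35 + 85 × 0.15 = 42.5. With arm, age and BMI as three terms that is about 14 per term, enough for a model of this size.

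**The case against.** The strongest case is that nothing here is wrong. An unadjusted chi-square is valid in a two-arm randomised trial, it is the test on which the sample size rests, and that size reproduces. No stratification is named, so the design creates no duty to adjust. All of this stands.

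Next, prognostic value is assumed. No section says that age, weight or height predicts intubating conditions. Section 4.2 speaks of variable response without tying it to age or body size, weight already enters the dose, and section 7.2 excludes severe renal impairment, end-stage liver disease and neuromuscular disease, which removes some heterogeneity. This also stands, and it is why a gain can only be called possible.

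A reader might infer that chance imbalance in age or body size would distort the result. The documents do not support that: random imbalance is already covered by the 5% error rate, and it matters for precision only if the covariate is prognostic. A reader might also infer that the missing interval follows from the lack of adjustment. It does not; an unadjusted risk difference with a 95% CI would supply it.

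Finally, if waiting for TOFC=1 individualises timing, covariates might matter less in that arm, and a simulation with equal effects in both arms could flatter adjustment. This was tested with effects mainly in the two-minute arm, and no loss was seen.

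**Conclusion.** The point holds as an improvement, not as an error. It is firm on the documents that the plan has one unadjusted test, no effect estimate, no interval, and three recorded baseline values that it does not use. The interval half-width of about 13 to 14 points needs no outside figure beyond the assumed rates.

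The gain from adjustment is uncertain. It runs from nil, or a trivial loss (variance ratio about 1.01 to 1.03), to a few points of power if age and BMI are moderately to strongly prognostic; the most extreme setting tried gave about 6 points. This assumes a main-effects logistic model that is roughly right and 85 analysable patients per group.

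Two stronger readings are not supported: that the trial is underpowered as planned, and that precision is certainly lost. The first fails because 83 per group reproduces, the second because the documents give no prognostic strength.

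**What to change.** Before data are seen, replace the sentence in section 9.1.1 with wording to this effect: the primary estimate is the difference in the proportion with score 3 (TOFC=1 minus 2 minutes) with a two-sided 95% CI and p-value, from a logistic regression on arm, age and BMI (computed from recorded weight and height, both covariates continuous), standardised over the whole sample to a marginal risk difference with a robust standard error. Report the unadjusted chi-square and the unadjusted risk difference with its 95% CI alongside, and say whether the chi-square uses a continuity correction, since the stated 83 per group matches the corrected version.

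Score 3 is taken from section 9.1. Section 6.4 says instead that the composite score will be compared; that is a separate ambiguity to settle in the same edit.

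The cost is a paragraph of SAP text and a few lines of code, with no new data. The downside is a negligible loss of precision if the covariates are useless, and a type I error of up to about 5 to 6% at this size, which a small-sample correction to the robust standard error can limit. If the team prefers not to adjust, the unadjusted risk difference with its 95% CI still answers the first half of the point.
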